### 8.2.6. Study Period

According to the overall timeline of the study, First Patient In (FPI) will start on 23 February, 2016, and Last Patient Last Visit (LPLV) will end on 30 December, 2016. Data collection will be finalized during this period.

For each patient, the study period is from the time when patient signs informed consent form to the time the study is closed. Patients' information will be collected at baseline visit, week 12 (D85,  $\pm 10$  days), and any unplanned visits (if occurrence). The study will be regarded as close when patient completes all the visits or withdraws from the study.

For adverse events, the reporting period begins at the time of the patient's first dose of atorvastatin or the time of the patient's informed consent if s/he is already exposed to atorvastatin, and lasts through the end of the observation period of the study, which should include 28 calendar days following the last administration of a drug under study

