#### 8.1.2. Study Endpoint

- **Primary endpoint**

- Achievement rate of LDL-C goals at 12 weeks of therapy of Atorvastatin according to Chinese Guideline on Dyslipidemia Prevention and Treatment in Adult (2007 version). It will be presented with the proportion of patients who achieve the LDL-C goal value. LDL-C target value for the patients with different risk level is defined in the [section 8.2.5](#) per guideline.

$$\text{Achievement Rate} = \frac{\text{No. subjects who achieve LDL-C target value}}{\text{No. subjects who complete 12-week follow up}}$$

- The time of 12-week will be calculated from the day when each patient starts taking atorvastatin. .
- Achievement rate will be summarized overall, within each risk strata, and by dose within each risk strata. 95% confidence intervals will be provided.

- **Secondary endpoint**

- Dosage distribution of Atorvastatin in cardiology patients with different risk stratification at the end of 12-week follow-up
- Safety and tolerability will be evaluated by recording the incidence and severity of adverse events, abnormal physical examination findings, and abnormal laboratory values through 12 weeks of treatment. Especially monitoring the patients who have any the following events:
  - Having muscle symptoms such as myalgia, fatigue, weakness, creatine kinase values 10 times the upper limit of normal, or rhabdomyolysis,
  - Having persistent elevation in alanine aminotransferase, aspartate aminotransferase, or both (defined as two consecutive measurements obtained 4 to 10 days apart that is more than three times the upper limit of the normal range).

- Major adverse cardiovascular events will also be recorded as adverse events, including death, myocardial infarction, stroke, documented unstable angina requiring re-hospitalization, revascularization with either percutaneous coronary intervention or coronary-artery bypass grafting.

Adverse events will be summarized overall and by dose within each risk strata.

- Dropout percentage and reason through 12 weeks of follow-up;

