### **8.2.3. Exclusion Criteria**

Patients meeting any of the following criteria will not be included in the study:

- Patients who have regularly taken atorvastatin therapy more than 4 weeks before enrollment

- Concomitant any other lipid-lower medication at baseline, or during the study conduction on physician clinical judgment

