### **Reporting period**

For each patient, the safety event reporting period begins at the time of the patient's first dose of atorvastatin or the time of the patient's informed consent if s/he is already exposed to atorvastatin, and lasts through the end of the observation period of the study, which must include at least 28 calendar days following the last administration of a drug under study; a report must be submitted to Pfizer Safety (or its designated representative) for any of the applicable types of safety events listed in the table above occurring during this period. If a patient was administered a drug under study on the last day of the observation period, then the reporting period should be extended for 28 calendar days following the end of observation. Most often, the date of informed consent is the same as the date of enrollment. In some situations, there may be a lag between the dates of informed consent and enrollment. In these instances, if a patient provides informed consent but is never enrolled in the study (e.g., patient changes his/her mind about participation), the reporting period ends on the date of the decision to not enroll the patient.

If the investigator becomes aware of a SAE occurring at any time after completion of the study and s/he considers the SAE to be related to atorvastatin, the SAE also must be reported to Pfizer Safety.

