5.2 SAFETY ANALYSIS SET (SAS)

The Safety Analysis population will include all patients who receive at least one dose of study drug atorvastatin. The SAS will be the primary analysis population for all safety reporting.

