11 APPENDICES

11.1 APPENDIX 1: DATA DERIVATION DETAILS

A1.1 Definition of visit windows

- Baseline (Day 1) is defined after informed consent date signed within one month prior to receive a study drug.
- Study Day = date of assessment – date of first dose of study drug + 1
- Week 12 is defined as Study Day 85 ± 28 days from the Day 1 study drug taken.
- Duration of Study Drug = Date of last dose – date of first dose +1
- End of Study: The Day completion of the study or discontinuation from the study.

A1.2 Demographic and Baseline Variables

- Demographic information : age, gender, height , body weight and BMI
- Medical histories:current or previous medical history, family history of premature atherosclerotic cardiovascular disease (ASCVD) and history of smoking
- Baseline Variables: strata
 - CVD risk level: low, moderate, high, very high, per definition in section 5.4.
 - Liver function tests: ALT, AST, total bilirubin (TBil)
 - Renal function tests: Creatinine (Cr), Blood Urea Nitrogen (BUN), Uric Acid (UA)
 - Serum lipid parameters :LDL-C, HDL-C, TG, Total-C
 - Creatine kinase value (CK)
 - Disease type: established CHD (Coronary Heart Disease), multiple risk factors, and hypercholesterolemia

A1.3 Definition of Derived Variables

Age

- Age = integer of [(informed consent date – date of birth)/ 365.25]
- Age groups: 18 – 64 years old, ≥ 65 years old

Body Mass Index (BMI)

- $BMI = \text{Weight (kg)} / [\text{Height (m)}]^2$

CVD risk level (strata)

The CVD risk level is based on Chinese Guideline on Dyslipidemia Prevention and Treatment in Adult (2007), the cardiovascular disease (CVD) risk stratification. The 10 years CVD risk factors are calculated based on age, sex, total cholesterol, HDL-C, hypertension, smoking history, medical history, and family history.

The CVD risk level for dyslipidemia will be derived.

Reference Normal Laboratory Ranges

The normal laboratory ranges will be defined by local lab facilities.

A2.1 SAS code for exact method

```
proc freq data=Lipitor order=freq;  
  tables LDL-C Goal / binomial (exact) alpha=.05;  
  title 'Exact methods of 95% confidence interval (CI) for rate of LDL-C' ;  
run;
```

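### For patients already on atorvastatin at consent, adverse events before consent are not collected, yet they are pooled in 12-week percentages counted from first dose

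*Protocol*

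**What the plan says.** - **Entry.** Protocol 8.2.3 excludes "Patients who have regularly taken atorvastatin therapy more than 4 weeks before enrollment". Shorter use is allowed. Protocol 8.2.2 asks only that laboratory reports from the month before starting, or from the 24 hours after, can be traced. A patient already on treatment can meet that.
- **Start of collection.** Protocol 8.2.6 begins adverse event reporting at first dose, or at "informed consent if s/he is already exposed to atorvastatin". Section 10 (Reporting period) says the same: "the safety event reporting period begins at the time of the patient's first dose of atorvastatin or the time of the patient's informed consent", the second option again being for patients already exposed. Under 8.2.6, "the study period is from the time when patient signs informed consent form to the time the study is closed".
- **Clock.** Protocol 8.1.2: "The time of 12-week will be calculated from the day when each patient starts taking atorvastatin". SAP Appendix 1 (A1.1): "Study Day = date of assessment – date of first dose of study drug + 1". The safety endpoint covers adverse events, "abnormal physical examination findings, and abnormal laboratory values through 12 weeks of treatment".
- **Denominator.** SAP 5.2 counts "all patients who receive at least one dose of study drug atorvastatin". SAP 8.2 summarises adverse events and adverse events of special interest (AESI) overall and by dose group within risk level. The subgroups in SAP 5.4 do not include exposure at consent, and no person-time or delayed-entry method is given.
- **End of collection.** Protocol 8.2.6 and section 10 carry reporting to 28 days after the last dose. SAP 8.2 sets no 12-week cut for the adverse event tables.
- **A conflicting definition.** SAP A1.1 describes baseline as falling after consent and before study drug, which reads as if nobody is treated before consent.

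**The concern.** For an already exposed patient the percentage has two different origins. The risk period starts at first dose and collection starts at consent. Any event in between happened on treatment, belongs to the endpoint, and is not asked for. The SAP's treatment-emergent definition (6.2) also runs from the start of treatment, so it presupposes observation that these patients do not have.

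There is also a selection element. A patient who stopped atorvastatin before consent is unlikely to be enrolled, and one who died before consent cannot be.

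Safety is a stated secondary objective, and Protocol section 6 justifies the study partly by the lack of safety data in Chinese patients. A reader of the pooled tables would take them as the 12-week experience of patients starting atorvastatin. For part of the cohort they may describe only those who reached consent, observed from that point.

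**Working it through.** **What the plan gives.** There is no expected adverse event rate, no share of patients exposed at consent and no lag, so there is no plan figure to reproduce for this point. The sample size rests on the LDL-C proportion (60%, ±1.1%, 7600 inflated to 10,000) and is not affected.

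**Direction.** Let S(t) be the probability of no event by day t after first dose, and L the day of consent.

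- True 12-week risk: 1 − S(84).
- Patient entering event-free at day L: observed risk 1 − S(84)/S(L). Because S(L) ≤ 1, this cannot exceed 1 − S(84), whatever the hazard shape.
- If an earlier event does not bar entry but is not recorded, the observed share with a first event is S(L) − S(84), which also cannot exceed 1 − S(84).

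With a cut at 12 weeks from first dose, the error can therefore only be downward.

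**Illustrative size, constant hazard, cut at day 84.** Assumed: true 12-week risk 10%, entry at day 28 (the longest lag allowed).

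- Days observed: 84 − 28 = 56, so 28/84 = 33% of the window is lost.
- Observed risk: 1 − 0.90^(56/84) = 6.8%. Relative loss: 1 − 0.0678/0.10 = 32%.
- Pooled with new starters, for an assumed share f entering at day 28, f × 6.78% + (1 − f) × 10%:

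| f | Pooled | Relative shortfall |
|---|---|---|
| 25% | 9.2% | 8% |
| 50% | 8.4% | 16% |
| 75% | 7.6% | 24% |

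**Sensitivity to the assumptions.**

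- Shorter lag, constant hazard: entry at day 7 gives 1 − 0.90^(77/84) = 9.2%, and entry at day 14 gives 1 − 0.90^(70/84) = 8.4%.
- Half of the events in the first 28 days: an event-free entrant at day 28 shows 5/95 = 5.3%, a 47% loss. The pooled shortfall is then about 12%, 24% or 36% for the same three shares.

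**Without the cut.** If a patient is still on drug at 12 weeks, reporting can run to day 84 + 28 = 112. On the same constant hazard:

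- New starter, 112 days observed: 1 − 0.90^(112/84) = 13.1%.
- Day-28 entrant, 112 − 28 = 84 days observed: 10.0%.
- Half and half: (13.1% + 10.0%)/2 = about 11.6%.

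That pooled figure is above the true 12-week risk of 10% and below the 13.1% that new starters show over the same calendar of treatment. It estimates neither.

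**The case against.** **Reporting continues past 12 weeks.** This is the strongest objection. Reporting runs 28 days beyond the last dose and the SAP makes no 12-week cut, so a late entrant can be observed for as many days as the endpoint requires. A reader might infer that the pooled percentages in the final tables must be about a third too low, or fall below the true 12-week risk. The documents do not support that: the illustrative losses hold only if events are cut at day 84, and without a cut the pooled figure can exceed the 12-week risk. What remains is that the extra late time does not recover early events, and that the windows are unequal.

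**The exposed share may be small.** Both schedules put consent at Baseline Day 1, and the SAP's study-day formula makes Day 1 the day of first dose. Few patients may be pre-exposed, and the shares used above are assumptions. The exclusion wording can also be read as duration or as timing, although either reading admits a patient who started within the last 4 weeks. This limits the size, not the direction.

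**Some early information survives.** Baseline laboratory values come from before treatment or within 24 hours of starting, so an enzyme or creatine kinase rise that persists past consent can still be seen. Atorvastatin duration and dose changes with reasons are also recorded. Events that resolved before consent are still lost. That early stoppers do not enrol is likely, but no criterion says so.

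**Dropout and LDL-C.** A reader might extend the point to both. The reporting rule governs adverse events only. Dropout is defined through 12 weeks of follow-up and the study period starts at consent, so nobody can drop out earlier. The LDL-C analysis set already requires completed 12-week follow-up, and no separate effect on that rate has been shown. A reader might also assume that muscle symptoms cluster in the first weeks, but the documents do not say so.

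**Safety is descriptive.** True, but a descriptive percentage still needs a defined risk period.

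**Conclusion.** The point holds for adverse events and AESI. The protocol admits patients already on atorvastatin and collects their events only from consent, while the endpoint and the SAP count from first dose over all treated patients with no adjustment. Measured through 12 weeks from first dose, the pooled incidence can only err low.

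The size cannot be determined from the documents. The range of 8% to 24% relative shortfall rests on a constant hazard, a true risk of 10%, a cut at day 84, and 25% to 75% of patients entering at day 28. With few exposed patients or short lags it would be small, and with front-loaded events larger. As the SAP stands, with no cut, the more certain defect is that the pooled percentage mixes unequal observation windows and has no clear 12-week meaning. No bias in dropout or in the primary LDL-C endpoint is established. This is a worthwhile, low-cost improvement to the safety analysis.

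**What to change.** In SAP 8.2:

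1. Report the distribution of the lag from first dose to consent and the number of patients already exposed at consent.
2. Tabulate adverse events and AESI separately for patients who consented on or before first dose (new starters) and for those already exposed.
3. Take the 12-week incidence from the new starters, with events cut at 12 weeks from first dose.
4. For the already exposed, give events per patient-week from consent.
5. Dropout may be shown by the same split, as description only.

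The baseline wording in SAP A1.1 should be reconciled with Protocol 8.2.3, 8.2.6 and section 10, which provide for treatment before consent.

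**Cost.** Extra table columns and no new data: A1.1 already uses the first-dose date for study day, and A1.3 uses the consent date for age. The new-starter incidence rests on fewer patients. As an illustration at 10% incidence, the approximate 95% half-width goes from 1.96 × √(0.09/10,000) = 0.6 percentage points to 1.96 × √(0.09/5,000) = 0.8 points if half of the 10,000 are new starters.

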### 8.2.7. Study Procedures

At baseline visit, patient inclusion/exclusion and demographic information, medical history, medication records, concomitant drugs and laboratory examination results prior to Atorvastatin therapy such as liver function, blood lipid parameter, creatine kinase value and renal function will be collected by investigators in the study. At week 12 visit and any unplanned visits, the laboratory examination results and medication records will be collected. Adverse events will be recorded at any time during the study period.

Schedule of Activities is as follows:

Protocol Activity	Visits	Visit 1	Visit 2	Any unplanned Visits
		Baseline Day(D)1	Week 12 D85 ( $\pm 10$ days)	Any date during Week 4 to Week 16 D29~D115( $\pm 10$ days)
Signed Informed Consent Form		▲		
Demographic information		▲		
Medical history		▲		
Laboratory examination		▲*	▲	▲
Inclusion/exclusion criteria		▲		

Visits	Visit 1	Visit 2	Any unplanned Visits
Adverse event records	Record at any time during the study period		
Medication records	▲	▲	▲

Notes: Each activity refers to section **8.3 Variables**

\* The date of the report should be within 1 month before taking atorvastatin or within 24h after starting atorvastatin therapy

### 8.2.8. Study Drug

The drug used in this study should be paid by patients themselves and administration method should be referred to the doctor's prescription.

### 8.3. Variables

This study will collect and analyze the effectiveness and safety data from approximately 10,000 eligible subjects from the time of first subject first visit to the time the study is closed. Since this is primarily an observational study, patient subsequent visits are set according to the return dates in clinical practice, which are supposed to be week 12 and any unplanned visits during week 4 to week 16.

- Demographic information includes patients' birth date, gender, body height and weight;
- Medical history includes information on current medical history, previous medical history, family history of premature cardiovascular disease and history of smoking ;
- Laboratory examination includes liver function [ ALT, AST, total bilirubin (TBil)], serum lipid parameter (LDL-C, HDL-C, TG, Total-C), creatine kinase value (CK) and renal function [creatinine (Cr), blood urea nitrogen (BUN), uric acid (UA)];
- Major adverse cardiovascular events including death, myocardial infarction, stroke, documented unstable angina requiring re-hospitalization, revascularization with either percutaneous coronary intervention or coronary-artery bypass grafting
- Other adverse events. (Details in [Section 10](#) MANAGEMENT AND REPORTING OF ADVERSE EVENTS/ADVERSE REACTIONS)
- Medication record: dosage and duration of Atorvastatin, as well as any dose change including reasons will be recorded.
- Concomitant drugs: antiplatelet drugs, angiotensin converting enzyme inhibitors (ACEI)/ angiotensin receptor blockers (ARB),  $\beta$ -block, diuretics and calcium antagonist are concomitantly used or not.

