2.1 STUDY DESIGN

Overview

This is a multi-center, prospective, observational study, which will be completed by Beijing Anzhen Hospital, Capital Medical University and approximately 64 other clinical sites.

At baseline visit, patient inclusion/exclusion and demographic information, medical history, medication records, concomitant drugs and laboratory examination results prior to atorvastatin therapy such as liver function, blood lipid parameter, creatine kinase value and renal function will be collected by investigators in the study. At week 12 visit and any unplanned visits, the laboratory examination results and medication records will be collected. Adverse events will be recorded at any time during the study period. Schedule of Activities is as follows:

Table 1: Schedule of Activities

Visits	Visit 1	Visit 2	Any unplanned visits
Protocol Activity	Baseline Day 1	Week 12 Day 85 (± 28 days)	Any Date During Week 4 to Study Close
Signed Informed Consent Form	▲		
Demographic information	▲		
Medical history	▲		
Laboratory examination	▲*	▲	▲
Inclusion/exclusion criteria	▲		
Adverse event records	Record at any time during the study period		
Medication records	▲	▲	▲

* The date of the report should be within 1 month before taking atorvastatin.

Study population

Judged by investigators, patients in cardiology department who are eligible for inclusion and exclusion criteria can be included into this study. Estimated total sample size is 10,000 and will be conducted in approximately 65 hospitals in China.

Data source

This Non-Interventional (NI) study data will be recorded in the medical records by investigators, and then input to electronic Data Collection (EDC) system as the form of electronic Case Report Form (eCRF).

Treatment/dose group

The study drug (atorvastatin) is from the doctor's prescription and will be recorded on Day 1, Week 12, and within Week 4 to end of the study. The analysis by dose groups will be taken the dose level recorded at Week 12 (Visit 2) on the prescription level or the last dose in the unplanned visit if the Week 12 is not available.

The dose groups will be in four daily dose levels, 10 mg, 20 mg, 40 mg and > 40 mg.

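### Laboratory values from about the first four weeks of treatment have no defined collection slot, so early CK or ALT/AST elevations that are not adverse events drop out of the laboratory proportions

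*Protocol*

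**What the plan says.** Protocol 8.2.7 names the occasions for post-baseline laboratory data: "At week 12 visit and any unplanned visits, the laboratory examination results and medication records will be collected". Its Schedule of Activities dates the unplanned visits "Any date during Week 4 to Week 16 D29~D115", with a 10-day tolerance printed after the range. Protocol 8.3 gives the same range ("which are supposed to be week 12 and any unplanned visits during week 4 to week 16"). SAP 2.1, Table 1 keeps the Week 4 start, shows no tolerance for unplanned visits and has a different end: "Any Date During Week 4 to Study Close". Protocol 8.2.6 lists baseline, Week 12 and any unplanned visits as the collection points, with no lower limit on the last.

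Baseline laboratory reports must be dated "within 1 month before taking atorvastatin or within 24h after starting atorvastatin therapy". The safety endpoint in Protocol 8.1.2 includes "abnormal laboratory values through 12 weeks of treatment". It singles out CK at 10 times the upper limit of normal (ULN) and persistent ALT/AST elevation, defined as two consecutive values above 3 x ULN taken 4 to 10 days apart. SAP 6.2 lists both as abnormal laboratory data, separately from adverse events, and SAP 8.2 plans the percentage of patients with abnormal CK, AST and ALT.

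Adverse events are recorded at any time (Protocol 8.2.7). The medication record covers dose, duration and every dose change with its reason, without a time limit (Protocol 8.3).

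**The concern.** The endpoint starts with treatment, but the first dated opportunity to enter a post-baseline laboratory value comes several weeks later. A site that follows the schedule literally has nowhere to put a CK or transaminase result from, say, Day 14. A site that follows Protocol 8.2.6 would enter it. Sites therefore lack one rule, and the laboratory proportions would mix the two practices.

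Safety is a secondary objective, and the protocol's rationale cites safety concerns about high-intensity statin in Chinese patients. A proportion described as running through 12 weeks, but without early laboratory values, would look more reassuring than the medical records might support. The exposure is greatest for transaminases, because the SAP's adverse events of special interest have muscle, cardiovascular and death categories but none for the liver.

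**Working it through.** **Inputs.** Protocol 8.2.7: Week 12 = D85 ± 10 days; unplanned visits D29 to D115 (± 10 days); baseline laboratory report up to 24 hours after first dose. SAP Table 1 and Appendix A1.1: Week 12 = D85 ± 28 days; unplanned visits from Week 4.

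**1. Reproduce the printed days.** With first dose as Day 1, week w falls on day 7w + 1. Week 4 gives 29 and Week 12 gives 85, both as printed. Week 16 gives 113, whereas the protocol prints D115. That difference does not affect the early gap.

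**2. Find the earliest post-baseline slot.**
- Week 12 visit: 85 − 10 = D75 (protocol) or 85 − 28 = D57 (SAP).
- Unplanned visits: D29 read strictly, or 29 − 10 = D19 if the tolerance applies to the lower limit.

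The unplanned window opens first on either reading, so it sets the gap.

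**3. Size the gap over D1 to D85.**
- Strict: Days 2-28 = 28 − 2 + 1 = 27 days; 27/85 = 31.8%.
- With tolerance: Days 2-18 = 18 − 2 + 1 = 17 days; 17/85 = 20.0%.

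The 24-hour baseline allowance can run into Day 2. Counting Day 2 as covered gives 26/85 = 30.6% and 16/85 = 18.8%.

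**4. Trace four invented cases through the documents.**
- *Muscle pain and CK above 10 x ULN on Day 12, drug changed.* This meets the abnormal-test criteria in Protocol section 10 twice (symptoms; change in dosing). It must go on the case report form and belongs to the muscle category of special interest in SAP 6.2. It could be absent only from the separate CK laboratory proportion.
- *ALT above 3 x ULN on Days 14 and 20, no symptoms, no action, normal at Week 12.* The values are 6 days apart, so the laboratory definition is met. Section 10 says that repeating an abnormal test does not by itself make an adverse event, so none need be recorded unless the investigator or sponsor judges it one. With a D29 start neither value is collected. With a D19 start only the second is, and the pair is incomplete. The patient is not counted.
- *The same pair on Days 25 and 31.* With a D29 start only the second value is collected and the definition fails. With a D19 start both are collected and it is met.
- *Dose reduced on Day 12.* The medication record taken at Week 12 covers the change and its reason, and SAP 6.2 calculates total dose from Day 1.

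**5. Direction of the error.** Let N be the safety analysis set, x the patients who truly meet a laboratory definition by Week 12, and m those among them who go uncounted because a needed value predates the window. The reported proportion is (x − m)/N. Since m ≥ 0, this is at most x/N. SAP section 7 excludes imputation, so nothing restores m. The documents give no early-testing frequency or elevation rate, so m cannot be estimated.

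**The case against.** The strongest reply is that clinically relevant early findings are already captured. Adverse events have no Week 4 limit, all of them go on the case report form, and CK at 10 x ULN sits within the muscle category that SAP 8.2 tabulates. SAP 6.2 also says that new or worsened findings at post-baseline visits are reported as adverse events. This stands for symptomatic or acted-on abnormalities. It does not close the gap for the rest. The SAP sentence depends on a visit taking place, an adverse event term is not stated to feed the laboratory tables, and liver elevations have no special-interest category.

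A second reply is that no passage says earlier results are refused. Protocol 8.2.6 sets no lower limit, and the wording in 8.3 can be read as an expectation about return dates. This also stands. The gap is the absence of a defined slot, not a proven exclusion, and the documents describe no date check in the data system that would reject an early result. But three places give the Week 4 start, and the amendment log describes the schedule range as a time limit on unplanned visits.

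A third reply is that SAP 8.1 lists unscheduled results without summarizing them, so entering more would change nothing. The same sentence excepts results that qualify for a derived endpoint. The CK and persistent ALT/AST definitions fit that exception, although the SAP does not say so outright.

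A reader might also infer that early dose changes go unrecorded. The documents do not support this: the medication record has no time limit and is taken again at Week 12. A patient who changes dose early and never returns could still be missed, but through loss to follow-up rather than the window.

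**Conclusion.** The point holds for early laboratory values that do not qualify as adverse events. Followed as written, the schedule leaves 32% of the days to D85 without a defined laboratory slot, or 20% if the tolerance applies to D29. The CK and ALT/AST laboratory proportions can then be undercounted but not overcounted. That direction assumes that the denominator is the safety analysis set, as SAP 5.2 and 8.2 indicate, and that sites follow the Week 4 start rather than Protocol 8.2.6.

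A reader might take 20% to 32% as the share of elevations missed. It is a share of calendar time. It would equal a share of events only if testing and elevations were spread evenly over the 12 weeks, for which the documents give no data, and an elevation that persists until the window opens can still be collected. Nor does it follow that an early symptomatic CK elevation disappears from the safety report. The primary endpoint and the sample size are unaffected.

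**What to change.** Reconcile Protocol 8.2.6, 8.2.7 and 8.3 with SAP Table 1 so that CK, ALT and AST results obtained in routine care on any date after the first dose are entered, including retrospectively where the medical record holds them. Use one upper limit in both documents; it is now D115 ± 10 days in the protocol and study close in the SAP. State in SAP 8.1 that these unscheduled values feed the CK and persistent ALT/AST derived endpoints.

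If early results cannot be retrieved, label the laboratory proportions as covering Week 4 onward, and say whether that means D29 or D19.

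The cost is wording in both documents, any matching change to the electronic case report form, and some extra data entry. No test or visit is added, because only results already in the medical record are entered.
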